This proposed project aims to improve guideline-based asthma care using enhanced communication and screening tools, telemedicine and directly observed therapy of preventive medications in city schools. This intervention is designed to overcome key barriers to guideline-based preventive asthma care among minority, poor children in Rochester, NY. Web-based screening will be used to identify children with persistent or poorly controlled asthma and to send reports to the child's primary care doctor. Children in the SB-TEAM group will receive a telemedicine asthma assessment in school and be prescribed a daily preventive asthma medication to be taken through school-based directly observed therapy. Follow-up telemedicine visits will be completed to make dose adjustments and treatment revisions to optimize guideline based treatment. Intervention functions will be overseen by the asthma coordinator, a registered nurse with extensive training in pediatric asthma, as well as [name], MPH, the study's primary investigator. The overall aim of this study is to evaluate the use of the SB-TEAM intervention for improving guideline based care, enhancing adherence to effective preventive medications and at reducing morbidity among young urban children with asthma.

Study Design:

We propose a two-group randomized trial. Children in participating schools will be systematically screened for asthma severity or control using the web-based system, and 400 eligible children will be assigned randomly to either the SB-TEAM intervention (directly observed administration of preventive asthma medications in school and ongoing monitoring and tailoring of the care regimen using telemedicine) or the eUC comparison condition (asthma screening with symptom reports and guideline-based recommendations for preventive medications sent to the PCP, and systematic feedback to the PCP and caregiver to promote appropriate follow-up care). Randomization will be stratified by the use of preventive medication at baseline and a permuted block design will be used to assure an equal balance of children in each group over time. Following randomization, children will be followed prospectively and systematically for the remainder of the school year.

Subjects and Setting:

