Flagging and screening of potential participants will occur in several ways with the assistance of the school nurses, health aides and administrators (all referred to as “school nurses” below), the asthma coordinator, and the study team. To test this intervention as intended in a real-world setting, we anticipate that most of the flagging and screening will be conducted by the school nurse or asthma coordinator. The school nurses or asthma coordinator will systematically identify and screen children with persistent asthma through a previously-tested web application. The school nurse, asthma coordinator, or study team (as needed) will also conduct a more thorough screening survey to assess eligibility criteria for this study prior to enrollment. If children are found to have mild symptoms (and therefore are not eligible for the study), the children may be re-screened by the school nurse or asthma coordinator to re-assess asthma symptoms at a later time during the screening and enrollment period. Screening and enrollment will occur each year in a rolling fashion from late August through November to enroll all children prior to the onset of peak winter season.

Prior to flagging/screening, the RSCD screening forms and medical-alert forms will be used to populate a student registry into the secure web application. The school nurses may also add children into the registry based on the nurse’s knowledge of students’ health status at his/her school (i.e. if the child has frequent visits to the nurse’s office for asthma attacks). The school nurses may only view and edit information in the web application for children at their school.

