Potential benefits for participants of the randomized trial exist for both groups of children (SB-TEAM and eUC). The goal is for children in the SB-TEAM group to have improved symptom assessment, adherence

to preventive medications, and appropriate tailoring of therapy, thus they may experience less morbidity from asthma. Although children in the eUC group will not be receiving medication through school or telemedicine asthma visits, we will prompt their PCP to provide guideline based asthma care including prescription of the appropriate preventive medications and will provide regular reminders to PCPs and caregivers to care for the child's asthma. Improved asthma management should result in reduced morbidity for these children. Since the medications used in this study are safe and effective at the doses administered, and are strongly recommended by the national asthma guidelines, we anticipate that the intervention benefits will outweigh the minimal risk of participation.

11. Analysis

Sample Size:

This study is designed to have adequate power to detect the smallest clinically significant difference in mean SFDs post-intervention between the intervention and enhanced usual care groups. Based on our previous data, we estimate the pooled standard deviation of SFD at 2.8 and within-subject correlation at 0.3. Power was calculated for the intervention effect on SFD with at least two assessments for each subject. We anticipate <15% attrition, as attrition was minimal (<10%) in the prior study, and therefore plan to enroll 400 children. With a final sample of 336, we will have 90% power to detect a difference of 0.8 symptom-free days or greater per 2-wk. period. This difference is supported by our prior data, and would justify continuing the intervention. There are more than 11,000 students in pre-k through 4th grade in the RCSD and at least 6,600 entering kindergarteners in a 3 year period. Conservatively assuming an asthma prevalence of 9%, more than 1,584 students have asthma, and approximately ½ of these students (792) have persistent asthma. In our prior study, we enrolled 74% of eligible subjects. A conservative estimate would allow us to enroll 120 subjects/year (60%), which is more than adequate to meet our sample size.

Primary Analysis:

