The primary analysis of this study aims to assess the effectiveness of the SB-TEAM intervention in reducing asthma morbidity (including symptom-free days post-intervention (follow-ups at 4 mo, 6mo and final) as the primary outcome) compared to an enhanced usual care comparison group in school age children with persistent asthma. We will follow subjects prospectively throughout the school year for clinical outcomes (symptoms, asthma control, health care use), functional outcomes (absenteeism, quality of life), and airway inflammation (FeNO). We will use graphical and numerical summaries to describe the outcomes at each assessment point. If distributional assumptions associated with a particular statistical procedure are violated, appropriate transformations will be made or non-parametric alternatives will be used. In accordance with the intention-to-treat principle, all randomized subjects will be analyzed within the group to which they were assigned; minimal crossover is expected. Hypothesis-driven comparisons will be made to control the family-wise type I error rate at 0.05 (two-sided) for the primary hypothesis.

We will determine whether there are important differences at baseline despite randomization between the SB-TEAM and eUC groups in demographics and background characteristics (age, race, ethnicity, insurance, caretaker education), depression, and cotinine. This will include t-tests (or Wilcoxon Rank Sum test) for continuous variables and chi-square (or Fisher's Exact) tests for discrete variables. These comparisons will enable the identification of control variables for use in analyses evaluating treatment effect.

To test for differences between the SB-TEAM and eUC groups on clinical and functional outcomes at the primary time point, bivariate comparisons will be made using t-tests for continuous variables (number of symptom-free days (SFD), symptom nights, rescue medication use, days absent, quality of life, FeNO,

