and ACT scores), and chi-square tests for discrete variables (acute visits, hospitalizations). In addition, the time-course of treatment response during the follow-up period will be evaluated using a linear mixed model with the primary outcome, SFD at post-intervention, as the response, and treatment condition, treatment by time interaction as independent variables. We will model the repeated assessment post-intervention and assess post treatment effects as well as maintenance gain during the period using appropriate linear contrasts. The analysis will be controlled for baseline symptoms, and variables that are found to differentiate between groups at baseline. The treatment effect will be regarded as fixed and the subjects will be modeled as random effect, with an appropriate variance covariance structure specified. Secondary continuous outcomes will be analyzed in a similar manner. Discrete outcomes will be analyzed by fitting Generalized Estimating Equation model. Appropriate link functions and response probability distributions will be specified.

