Cost Effectiveness Analysis: *Establish the cost-effectiveness of the intervention with a specific focus on ultimate sustainability and dissemination.* We will assess health and economic benefits of SB-TEAM from both the societal and the Medicaid perspective. We also will use *Diffusion of Innovations Theory* to help understand how this innovative model can be maintained in the current system of care through city schools.

We will assess health and economic benefits of SB-TEAM compared to enhanced usual care by using cost-effectiveness (CE) methodology. The time horizon of the study will be one school year (September-June). Four cohorts that will complete the study in consecutive years will be analyzed as one stacked study cohort. The basecase analysis will be conducted from the societal perspective which includes all identifiable costs and benefits, regardless of whom they impact. The majority of children in the study

are eligible for Medicaid (73% based on the prior study), thus a second analysis will take the Medicaid perspective. The benefits of the intervention will be measured as the number of symptom-free days during the school year.

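### Randomization is blocked over time, but the covariate rule in effect keeps school-year cohort and enrolment date out of the SFD model, at a modest cost in precision

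*Combined protocol and SAP*

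**What the plan says.** **Design.** Study Design, and again section 3 (Randomization), say that "a permuted block design will be used to assure an equal balance of children in each group over time". The only stratification factor is use of a preventive medication at baseline, and no block size is given. Subjects and Setting spreads recruitment over four school years (2012-2016). Section 1 (Flagging and Screening Procedures) adds: "Screening and enrollment will occur each year in a rolling fashion from late August through November". It ties this window to enrolling children ahead of the winter peak. Section 4 (Follow-Up Assessments) sets follow-up at 7 to 9 months depending on when a child enrols, with the last visit at the close of the school year.

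**Analysis.** Section 11 (Primary Analysis) names treatment and treatment by time as terms of the linear mixed model for SFD, with a random subject effect. On covariates it says: "The analysis will be controlled for baseline symptoms, and variables that are found to differentiate between groups at baseline". The baseline comparisons listed there cover age, race, ethnicity, insurance, caretaker education, depression and cotinine. Cohort and enrolment date are not among them, and neither of these nor the stratification factor is named as a model term.

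**The concern.** Blocking over time improves precision only if the analysis reflects it. Here the two work against each other: the design removes imbalance in time, and the covariate rule adjusts only for imbalance. If SFD differs between school years, or between children enrolled in late August and in November, both arms share that variation about equally. It does not distort the difference between arms, but with no term for it in the model it is counted as unexplained variation between children. At stake is the width of the confidence interval for SFD and for the continuous secondary outcomes.

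**Working it through.** **1. Inputs from section 11.**
- Type I error: "control the family-wise type I error rate at 0.05 (two-sided) for the primary hypothesis".
- Variability: "we estimate the pooled standard deviation of SFD at 2.8 and within-subject correlation at 0.3".
- Assessments in the power calculation: "with at least two assessments for each subject".
- Target: "With a final sample of 336, we will have 90% power to detect a difference of 0.8 symptom-free days or greater per 2-wk. period".
- Primary Analysis lists three post-intervention assessments (4 months, 6 months, final).

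**2. The plan's own figure.** The variance of a child's mean over m assessments is 2.8² × (1 + (m − 1) × 0.3)/m.
- For m = 2: 7.84 × 0.65 = 5.096, SD 2.257. Then n per arm = 2 × (1.960 + 1.282)² × 5.096/0.8² ≈ 167.3, rounded up to 168. The total is 336 and power is 90.1%, so the stated figure reproduces with no credit for covariates.
- For m = 3: 7.84 × 1.6/3 = 4.181. Power with 168 per arm is 94.8%.

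**3. Would the rule ever select these variables?** A simulation used 336 children, four equal cohorts, uniform enrolment within each window, two strata (assumed 60:40) and block sizes 4, 6, 8 and 10, with 3,000 runs for each size. Cohort differed between arms at p < 0.05 in no run (smallest p 0.57, at block size 10). Enrolment date did so in at most about 0.1% of runs.

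**4. Cost of leaving them out.** Let r be the share of SFD variance that cohort and enrolment date explain beyond visit time and baseline symptoms, constant over a child's visits. The documents do not give r; 1% to 10% is assumed. The 95% half-width with 168 per arm is 1.96 × √(2 × (V − 7.84r)/168), where V is the variance from step 2.

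| r | SD of the time effects (√(7.84r)) | m = 2: half-width | unadjusted wider by | m = 3: half-width | unadjusted wider by |
|---|---|---|---|---|---|
| 0 (unadjusted) | – | 0.483 | – | 0.437 | – |
| 1% | 0.28 | 0.479 | 0.8% | 0.433 | 1.0% |
| 2% | 0.40 | 0.475 | 1.6% | 0.429 | 1.9% |
| 5% | 0.63 | 0.464 | 4.1% | 0.416 | 5.0% |
| 10% | 0.89 | 0.444 | 8.7% | 0.394 | 10.9% |

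For m = 2, power would move from 90.1% to 90.6%, 91.0%, 92.2% and 94.2% for the four shares.

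**5. Direction of the error.** In the same simulation at block size 4, type I error without the terms was 4.8%, 4.5% and 3.5% for r = 2%, 5% and 10%, against 5.1% with them. The simulation standard error is √(0.05 × 0.95/3000) ≈ 0.4 points, so only the larger shares stand clear of noise. The direction is conservative.

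**6. Cost of adding them needlessly.** With r = 0 at block size 4, the mean half-width was 0.4843 without cohort and enrolment date and 0.4845 with them.

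**The case against.** **Much of the season is already in the model.** This stands. Treatment by time, read as bringing visit time with it, takes up the common course over the year, and every child's final visit is at the end of the school year. Baseline symptoms may absorb more. What is left is differences between years and the roughly three-month calendar spread of the 4- and 6-month visits. Under an assumed annual sine curve, that spread gives the three-visit mean an SD of at most about a quarter of the seasonal amplitude. An SD of 0.28 (the 1% row) would then need a peak-to-trough swing of at least 2 × 0.28/0.25 ≈ 2.2 SFD per two weeks. An SD of 0.63 (the 5% row) would need about 2 × 0.63/0.25 ≈ 5.0. The higher rows therefore rest mainly on year effects, for which the documents give no evidence.

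**The design was not sized on this gain.** This also stands. A reader might infer that the trial is underpowered or its treatment effect biased. Neither follows: 336 reproduces without these terms, and the blocks protect the comparison.

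**The rule does not forbid these covariates.** True as wording, since the covariate list is not expressly closed. In practice, selection by imbalance will not pick up a factor that the blocks have balanced.

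**Stacking the cohorts.** The statement "Four cohorts that will complete the study in consecutive years will be analyzed as one stacked study cohort" might be read as a decision to ignore cohort in the SFD model. It belongs to the Cost Effectiveness Analysis and does not govern the mixed model.

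**The gain does not reach every outcome.** Correct. Acute visits and hospitalizations are analysed by GEE. With a logit link, covariate adjustment changes the odds ratio being estimated and need not narrow its interval, and sparse events can make the fit unstable.

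**Conclusion.** The point holds as a minor, nearly free improvement in precision. The blocking and the covariate rule do not match, and cohort and enrolment date will practically never enter the model. If they explain an assumed 1% to 5% of SFD variance after visit time and baseline symptoms, the interval is about 1% to 5% wider than needed. At 10% it would be about 9% to 11% wider, but nothing in the documents points to a share that large. Inference is slightly conservative and unbiased, and the stated sample size and power are unaffected. The size rests wholly on the assumed share and on its being constant over visits. That some such variation exists is plausible, since the protocol itself times enrolment around the winter peak, but it is not documented.

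**What to change.** In section 11, Primary Analysis, prespecify these fixed covariates in the linear mixed model for SFD, regardless of baseline balance:
- school-year cohort (4 levels);
- enrolment date, continuous, in days from the start of that year's enrolment. Month categories are less suitable, because with a late August start the August level could be nearly empty;
- baseline preventive medication use, the stratification factor.

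Use the same terms in the models for continuous secondary outcomes. Do not extend them automatically to sparse discrete outcomes such as hospitalizations.

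The cost is one or two sentences in the plan and about 5 degrees of freedom (3 + 1 + 1) out of more than 330. Enrolment dates and the stratum are already recorded. If time explains nothing, the loss is negligible.

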held device that instantly analyzes exhaled air for NO concentration. Children will be asked to first fully exhale and then to take a fast and deep inhalation through a disposable mouthpiece attached to the device. Then, we will ask children to exhale slowly and steadily through the mouthpiece. If done correctly, a reading will appear on the screen which will be recorded manually. FeNO will be measured 3 times, once at the baseline visit, at 4-month follow-up, and then again at the end of the school year. Some children may have difficulty with this procedure; we will only include data for children who are able to perform the procedure accurately.

Secondary Smoke Exposure: Saliva Sample Collection for Measurement of Cotinine:

Exposure to secondhand smoke will be assessed by both interview survey and cotinine measurements. At the beginning and the end of the program, a member of the research team will collect salivary fluid samples from each child using the Sorbette fluid specimen collection device, which consists of a small sterile swab mounted on the end of a 5.5 cm plastic handle. Collection will be made according to a standard protocol developed for use with children. Salivary samples will be stored frozen and shipped via courier to Salimetrics, LLC in State College, PA for analysis. The cotinine results will be recorded as an outcome measure, and will be available to families only by request. However, all families will receive resources on how to stop smoking and prevent smoke exposure.

6. Compensation

Each participating parent will be paid \$20 after completion of the baseline assessment. Subjects will also be mailed \$20 after each of the telephone follow-up surveys and \$50 after the final follow-up survey. Total payment will be no more than \$130. Payment to participants will be in the form of a Wegman's grocery store gift certificate.

Healthcare providers who complete an evaluation at the end of the program will be mailed a \$5 Starbucks gift card to thank them for their time.

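### FeNO, ACT, quality of life and days absent are tested without baseline adjustment, and the plan does not say whether the added model uses each outcome's own baseline

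*Combined protocol and SAP*

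**What the plan says.** Section 11, Primary Analysis, of the combined protocol and SAP sets out two analyses of the continuous outcomes.

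- **Tests at the primary time point.** Here "bivariate comparisons will be made using t-tests for continuous variables". The outcomes listed are symptom-free days (SFD), symptom nights, rescue use, days absent, quality of life, FeNO and ACT. No covariate is attached to these tests.
- **A linear mixed model, in addition.** Its response is post-intervention SFD, with treatment and treatment-by-time terms. On covariates: "The analysis will be controlled for baseline symptoms, and variables that are found to differentiate between groups at baseline". The model is then extended: "Secondary continuous outcomes will be analyzed in a similar manner". The baseline covariate is not restated for any secondary outcome.

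The same section lists what will be compared between arms at baseline in order to find control variables: demographic and background items, depression and cotinine. FeNO, ACT, quality of life and absences are not on that list.

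The table in section 5 (Measures) schedules a baseline measurement of FeNO, ACT, PACQLQ and absenteeism. The FeNO subsection confirms this: "FeNO will be measured 3 times, once at the baseline visit". It adds that only children who can perform the test accurately contribute data.

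**The concern.** The first-named test of each of these outcomes ignores a baseline value that the trial collects. That holds on any reading of the later sentence about the model.

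The model may or may not repair this. Baseline symptoms are a natural adjustment for SFD. For FeNO or PACQLQ they are a different quantity from the outcome's own starting value. The other way in, as a variable found to differ between arms, is not open as written, because these measures are not among those to be compared.

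Three things are at stake, all in secondary outcomes:

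- intervals wider than they need to be;
- no correction for a chance baseline difference in the outcome itself;
- a choice between t-test and model, and between covariates, that could be made after the data are seen.

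**Working it through.** **Inputs from the documents**
- Two-sided 0.05. Section 11 sets this for the primary analysis, to "control the family-wise type I error rate at 0.05 (two-sided) for the primary hypothesis"; I use the same level for illustration.
- Variability, from section 11, Sample Size: "we estimate the pooled standard deviation of SFD at 2.8 and within-subject correlation at 0.3".
- The power calculation there assumes a minimum of two SFD assessments per child.
- The result that the section reports: "With a final sample of 336, we will have 90% power to detect a difference of 0.8 symptom-free days or greater per 2-wk. period".
- 1:1 allocation (section 3, Randomization), so 336 is 168 per arm.

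**Assumed inputs.** The documents give no correlation between baseline and follow-up for FeNO, ACT, PACQLQ or days absent. I use r = 0.3, 0.5 and 0.7. The only within-subject correlation given is 0.3, for SFD.

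**Step 1. Reproduce the plan's own figure.** The SD of the mean of two assessments is 2.8 × √((1 + 0.3)/2) = 2.257. The number per arm is 2 × (1.960 + 1.282)² × 2.257² / 0.8² = 167.3, so 168 per arm and 336 in total. Power at 168 per arm is 90.1%. The stated figure reproduces, and this point does not challenge it.

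**Step 2. Unadjusted against own-baseline adjustment, one time point, 168 per arm.**
- Unadjusted detectable difference at 80% power: (1.960 + 0.842) × √(2/168) = 0.306 SD.
- Adjustment multiplies the residual variance by 1 − r², so the detectable difference is 0.306 × √(1 − r²).

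| Assumed r | Variance reduction | Detectable difference | Power for an effect with 80% unadjusted |
|---|---|---|---|
| 0.3 | 9% | 0.292 SD | 83.6% |
| 0.5 | 25% | 0.265 SD | 89.9% |
| 0.7 | 49% | 0.218 SD | 97.5% |

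**Step 3. Against a model that already contains baseline symptoms.** Let s be the correlation of the outcome with baseline symptoms, and c that between the two baselines (both assumed). With both covariates, R² = (r² + s² − 2rsc)/(1 − c²). The further variance reduction is 1 − (1 − R²)/(1 − s²).

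| r | s | c | Residual variance, symptoms only | Residual variance, both | Further reduction | Power, from 80% |
|---|---|---|---|---|---|---|
| 0.3 | 0.15 | 0.3 | 0.978 | 0.906 | 7% | 82.9% |
| 0.5 | 0.2 | 0.3 | 0.960 | 0.747 | 22% | 88.8% |
| 0.5 | 0.3 | 0.5 | 0.910 | 0.747 | 18% | 87.1% |
| 0.7 | 0.2 | 0.3 | 0.960 | 0.510 | 47% | 97.0% |
| 0.7 | 0.3 | 0.5 | 0.910 | 0.507 | 44% | 96.4% |

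**Step 4. Chance imbalance.** The baseline difference between arms has standard error √(2/168) = 0.109 SD. A difference of 0.2 SD or more in either direction (0.2/0.109 = 1.83 standard errors) arises about 7% of the time per outcome. A difference of 0.2 SD shifts the unadjusted contrast by 0.2r, that is 0.06, 0.10 or 0.14 SD for r = 0.3, 0.5 or 0.7.

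For FeNO, 168 per arm is an upper guide, because children who cannot perform the test are left out. Detectable differences grow with 1/√n.

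**The case against.** The strongest reply is that the plan may already intend the right model. For SFD, baseline symptoms are broadly the baseline of the response, so handling the secondaries similarly can mean adjusting each for its own baseline. A reader might infer that these outcomes are never adjusted for their own baseline. The text neither names nor excludes that covariate, so the inference goes too far. What stands is that the model's covariate is unspecified and that the t-tests are unadjusted.

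Several further points stand:

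- Under randomization the unadjusted t-test is unbiased on average and keeps its type I error. Its standard error already allows for chance imbalance.
- For symptom nights, and arguably rescue use, baseline symptoms may already be the outcome's own baseline, so those two are left out of this point.
- For days absent, enrollment starts in late August and the recall period is not given. Baseline absence may therefore predict little, and the gain could be below the range shown.
- The 9% to 49% reductions compare with no adjustment at all. Against the symptom-adjusted model the range is about 7% to 47%, under further assumptions.
- No power is claimed for secondary outcomes, and the family-wise error control covers only the primary hypothesis.

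It can also be said that the t-test and the model will both be reported, so replacing one is a matter of taste. That does not stand: the plan does not say which one is the main result, and the test it names first is the less precise.

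**Conclusion.** The point holds as a loss of precision, together with an unspecified covariate. At 168 per arm and one time point, the detectable difference of 0.306 SD could be 0.292 to 0.218 SD, if the outcome correlates 0.3 to 0.7 with its own baseline. At the low end the gain is small. At the high end it is large. The documents cannot say where FeNO, ACT, PACQLQ or days absent fall.

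Two stronger readings are tempting and not supported. One is that the secondary tests are biased or invalid; randomization rules that out. The other is that FeNO is the trial's main objective outcome, so that its analysis carries special weight. No section ranks it so, and section 5 also lists spirometry, medical chart and pharmacy review, and school records.

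Nothing here shows a defect in the analysis of the discrete outcomes. The primary outcome, N = 336 and 90% power are untouched. The change is worth making before analysis because the baseline data are already being collected.

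**What to change.** In section 11, for FeNO, ACT, PACQLQ and days absent:

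1. State that the mixed model includes that outcome's own baseline value as a fixed covariate, on the same scale as the outcome (for example log FeNO at baseline if FeNO is analyzed on the log scale).
2. Make the adjusted treatment contrast at the primary time point the main result, in place of the t-test.
3. Keep children with a missing baseline value in the analysis, by a missing-indicator or a joint model, and say which. This matters most for FeNO.

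Section 3 places randomization after the baseline assessment, so these values precede treatment and can safely be adjusted for. The cost is SAP wording and a little analysis work; no new data, visits or children are needed.
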